9.3 Dose Modification

No dose reductions will be performed for hematological toxicities Grade 1 or 2 and non-hematological toxicities grade 1. No dose reduction of imatinib will occur during the first cycle for the Phase Ib patients.

9.3.1 Imatinib:

Please refer to Table 4 and 5 for dose reduction steps and criteria for interruption and re-initiation of imatinib for drug-related toxicities.

Table 4: Dose Modification Algorithm for Imatinib

Dose Level	Imatinib Dose
1	400 mg QD
-1	300 mg QD
-2	200 mg QD

MEMORIAL SLOAN-KETTERING CANCER CENTER
IRB PROTOCOL

IRB#: 14-140 A (7)

Table 5: Dose modifications for adverse events associated with imatinib

Hematologic toxicity	
≥ Grade 3	
Hold therapy and resume imatinib at 400 mg QD after recovery to ≤ Grade 2, if recovery occurs within 14 days
 
If toxicity persists for 15-28 days or recurs, hold therapy and resume at next lower dose level after recovery to ≤ Grade 2: I → 300 mg QD
 
If recurrence is seen at the reduced imatinib dose, hold therapy and resume at next lower dose level after recovery to ≤ Grade 2. I → 200 mg QD
 
If 4th occurrence, considerations should be had to remove subject from study if the toxicities are not manageable with appropriate supportive measures.

Note:
 
No dose reductions will be performed for grade 3 or 4 anemia. The patient may receive blood transfusions. Use of erythropoietin alfa (EPO) is allowed at the discretion of the treating investigator. G-CSF or GM-CSF may not be used as a prophylactic but may be used as otherwise clinically indicated to support blood counts for patients in this study.
	
General non-hematologic toxicity	
Grade 2 (intolerable or persisting > 7 days with optimal supportive care)	
Hold therapy and resume imatinib at 400 mg QD after recovery to ≤ Grade 1, if recovery occurs within 14 days
 
If toxicity persists for 15-28 days or recurs, hold therapy and resume at next lower dose level after recovery to ≤ Grade 1: I → 300 mg QD
 
If recurrence is seen at the reduced imatinib dose, hold therapy and resume at next lower dose level after recovery to ≤ Grade 1. I → 200 mg QD
 
If 4th occurrence, considerations should be had to remove subject from study if the toxicities are not manageable with appropriate supportive measures.

MEMORIAL SLOAN-KETTERING CANCER CENTER
IRB PROTOCOL

IRB#: 14-140 A (7)


≥ Grade 3
	
Hold therapy and resume imatinib at 300 mg QD after recovery to ≤ Grade 1, if recovery occurs within 14 days
 
If toxicity persists for 15-28 days or recurs, hold therapy and resume at next lower dose level after recovery to ≤ Grade 1:
 
I→ 200 mg QD
 
If recurrence is seen at the reduced imatinib dose, hold therapy and resume at next lower dose level after recovery to ≤ Grade 1.
 
I→ 100 mg QD
 
If 4th occurrence, considerations should be had to remove subject from study if the toxicities are not manageable with appropriate supportive measures.

------------------	---

Dose re-escalation

Every attempt to re-escalate the dose of study treatment to the initial dose level should be made. This applies to either dose reductions due to hematological or non-hematological toxicities. The dose should be re-escalated if the following criteria are met within 4 weeks after dose reduction:

- All ≥ Grade 2 non-hematologic toxicities have resolved to ≤ Grade 1
- All ≥ Grade 3 hematologic toxicities have resolved to ≤ Grade 1
- Or alternatively, all ≥ Grade 3 hematological and non-hematological toxicities have resolved to ≤ Grade 2 and are manageable with supportive therapy

Re-escalation of imatinib should be considered and are encouraged, especially if a participant undergoes one full cycle at the modified dose without experiencing the toxicity that caused the dose reduction.

MEMORIAL SLOAN-KETTERING CANCER CENTER
IRB PROTOCOL

IRB#: 14-140 A (7)

9.3.2 BGJ398:

For patients who do not tolerate the protocol-specified dosing schedule, dose adjustments are permitted in order to allow the patient to continue the study treatment. These changes must be recorded on the Dosage Administration Record CRF.

All dose modifications should be based on the worst preceding toxicity. The following guidelines need to be applied:

Each patient will be allowed up to 3 dose reductions, provided this is feasible based on the RP2D. Patients must discontinue BGJ398 if toxicities persist following 3 dose reductions (Table 6) unless a continuation is allowed in discussion with the MSKCC PI.

Following resolution of toxicity to baseline or \leq grade 1, treatment is resumed at either the same or lower doses of study drugs as per the criteria in Table 6. If treatment is resumed at the same doses of study drugs, and the same toxicity recurs with the same or worse severity regardless of duration, doses must be reduced to the next lower dose level (Table 6). If treatment is resumed at the lower doses of study drugs, and the same toxicity recurs with the same or worse severity, the patient must discontinue study treatment unless a continuation is allowed in discussion with the MSKCC PI.

If a patient requires a dose delay of > 14 consecutive days of BGJ398 from the intended day of the next scheduled dose, then the patient should be discontinued from the study treatment unless a continuation is allowed in discussion with the MSKCC PI.

In exceptional situations, study treatment may continue even if the patient experienced one of the treatment stopping rules. The decision to allow for continuation of treatment will be made on a case-by-case basis following discussion between the MSKCC Principal Investigator (MPI) and the Investigator. Situations that may allow for continuation of treatment include but are not limited to the following. A dose delay of > 14 days has occurred, but the patient is clearly benefiting from study treatment (i.e., stable disease, partial response, or complete response) and it is the investigator's opinion that no safety concerns are present, after discussion with the MPI, the patient may remain on the study treatment. A third or subsequent reduction (to dose level -3) in dose may be allowed if the patient is clearly benefiting from study treatment (i.e., stable disease, partial response, or complete response) but is experiencing adverse events that prevent continued treatment at the already reduced dose.

For guidance regarding interruptions in BGJ398 therapy due to adverse events, please see Table 7. Of special note is management of hyperphosphatemia, an expected on-target drug effect. See the Renal section of Table 8 for dose interruptions for acute kidney injury accompanied by hyperphosphatemia. Recommendations for prophylaxis and dose modifications for hyperphosphatemia are outlined in Table 8. Exact timing of stopping/starting BGJ398 in the setting of elevated phosphorous levels will be left to the judgment of the treating physician, and differences in phosphate management will not be considered protocol deviations. A list of high-phosphorous foods and suggested alternatives is provided in Appendix F to guide discussions regarding appropriate dietary intake. Please note plasma assessments may substitute for serum assessments per local laboratory standards.

MEMORIAL SLOAN-KETTERING CANCER CENTER
IRB PROTOCOL

IRB#: 14-140 A (7)

Table 6: Dose reduction table

Dose level	BGJ398	
Dose level 0	RP2D	Starting dose
Dose level -1	RP2D minus 25 mg	
Dose level -2	RP2D minus 50mg	
Dose level -3	RP2D minus 75mg	Allowed only if patients is clearly benefiting from study treatment, but is experiencing AE that prevent continued treatment at dose level -2 and applicable based on RP2D

Table 7: Criteria for interruption and re-initiation of BGJ398 treatment

Worst Toxicity CTCAE using the current active CTCAE version	Recommended Dose Modifications any time during a cycle of therapy
Cardiac disorders	
Cardiac - Prolonged QTc interval by Fridericia's Formula (QTcF)	
Grade 1 and 2 : QTcF 481-500 msec (asymptomatic)	Maintain dose level of BGJ398 
 ECG assessments should be performed for 2 additional cycles at the same frequency as in cycle 1, or as clinically indicated. If ECG assessments show no QTcF \geq 481 msec, for subsequent cycles ECG monitoring will be performed as per visit schedule. If ECG assessments are still abnormal (QTcF \geq 481 msec and \leq500 msec), then ECG monitoring must continue at the same frequency as in cycle 1 for all subsequent cycles.
Grade 3 : QTcF > 500msec as identified on the ECG by the investigator	
 Hold BGJ398. Monitor patient with hourly ECGs until the QTcF has returned to baseline. Perform further monitoring as clinically indicated. Exclude other causes of QTcF prolongation such as hypokalemia, hypomagnesaemia and decreased blood oxygenation. Patients should receive appropriate electrolyte replacement and should not receive further BGJ398 until electrolytes are documented to be within normal limits. 
Once the QTcF prolongation has resolved, patients may be re-treated at one lower dose level at the investigator's discretion

MEMORIAL SLOAN-KETTERING CANCER CENTER
IRB PROTOCOL

IRB#: 14-140 A (7)

Worst Toxicity CTCAE using the current active CTCAE version	Recommended Dose Modifications any time during a cycle of therapy
	
 • ECG assessments should be performed for 2 additional cycles at the same frequency as in cycle 1 or as clinically indicated 
 ○ If ECG assessments show no QTcF \geq 481 msec, for subsequent cycles ECG monitoring will be performed as per visit schedule. ○ If ECG assessments are still abnormal (QTcF \geq 481 msec and \leq500 msec), then ECG monitoring must continue at the same frequency as in cycle 1 or as clinically indicated, for all subsequent cycles • Patients who experience recurrent QTcF \geq 500msec after one dose reduction will be discontinued from study. 
NB: If ventricular arrhythmia or Torsades de Pointes is observed in a patient, he/she will be discontinued from the study.
 
Whenever QTcF \geq 501msec is observed, a plasma sample for determination of BGJ398 concentration should be obtained with the time of sample collection noted.

Cardiac disorders - others Grade \geq 3, or congestive heart failure \geq 2	Discontinue patient from study treatment.
Investigations-Hematology	
ANC decreased (Neutropenia) Grade 3 (ANC $<$ 1.0 - 0.5 x 10 ⁹ /L) Grade 4 (ANC $<$ 0.5 x 10 ⁹ /L)	Hold dose of BGJ398 until resolved to CTCAE Grade \leq 1 or baseline, then 
 • If resolved in \leq 7 days, maintain dose level of BGJ398 • If resolved in $>$ 7 days, \downarrow 1 dose level of BGJ398. Hold dose of BGJ398 until resolved to CTCAE \leq Grade 1, \downarrow 1 dose level of BGJ398.
Febrile neutropenia Grade 3 (ANC $<$ 1.0 x 10 ⁹ /L, single temperature of $>$ 38.3°C or a sustained temperature of \geq 38.0°C for more than one hour) Grade 4	Hold dose of BGJ398 until resolved to CTCAE Grade \leq 1, then 
 • If resolved by \leq 7 days, \downarrow 1 dose level of BGJ398. • If not resolved within 7 days discontinue patient from study drug treatment. Discontinue patient from study treatment.
Hemoglobin	Hold dose of BGJ398 until resolved to CTCAE Grade \leq

MEMORIAL SLOAN-KETTERING CANCER CENTER
IRB PROTOCOL

IRB#: 14-140 A (7)

Worst Toxicity CTCAE using the current active CTCAE version
	
Recommended Dose Modifications any time during a cycle of therapy

Grade 3 (<8.0 mg/dL – 6.5 mg/dL)
 
Grade 4 (< 6.5 mg/dL)
	
1 or baseline, then maintain dose level
 
Hold dose of BGJ398 until resolved to CTCAE Grade ≤ 1 or baseline, then ↓ 1 dose level

Platelet count decreased (Thrombocytopenia)
 
Grade 3 (PLT < 50 - 25 x 10⁹/L) without bleeding
 
Grade 3 (PLT < 50 - 25 x 10⁹/L) with bleeding or
 
Grade 4 (PLT < 25 x 10⁹/L)
	
Hold dose of BGJ398 until resolved to CTCAE Grade ≤ 1 or baseline
 
 • If resolved in ≤ 7 days, maintain dose level of BGJ398. • If resolved in > 7 days, ↓ 1 dose level of BGJ398 
Hold dose of BGJ398 until resolved to CTCAE Grade ≤ 1 or baseline, then ↓ 1 dose level

Investigations – Renal
	

Serum creatinine
 
Grade 1 and Ca x Pi >55 mg²/dl² despite sevelamer 1600 mg TID and low-phosphorous diet for at least 14 days
 
Grade 2 (> 1.5 - 3.0 x ULN) and Ca x Pi ≤55 mg²/dl²
 
Grade 2 and Ca x Pi >55 mg²/dl² despite phosphorus lowering therapy for at least 14 days
 
Grade ≥ 3 (> 3.0 x ULN)
	
Monitor Cr, Ca, and Pi at least twice weekly until Cr improves or stabilizes
 
Hold dose of BGJ398 until resolved to CTCAE Grade ≤ 1 or baseline
 
 • If resolved in ≤ 7 days, maintain dose level of BGJ398. • If resolved in > 7 days, ↓ 1 dose level of BGJ398. 
Hold dose of BGJ398 until resolved to CTCAE Grade ≤ 1 or baseline
 
 • If resolved in ≤ 7 days, maintain dose level of BGJ398. • If resolved in > 7 days, ↓ 1 dose level of BGJ398. 
Discontinue patient from study treatment
 
Discontinue patient from study treatment.

Investigations – Hepatic
	

Blood bilirubin (patients with Gilbert Syndrome these dose modifications apply to changes in direct bilirubin only)
 
Grade 2 (>1.5 – 3.0 x ULN)
	
Hold dose of BGJ398 until resolved to CTCAE Grade ≤ 1
 
 • If resolved in ≤ 7 days, maintain dose level of BGJ398. • If resolved in > 7 days, ↓ 1 dose level of BGJ398.

MEMORIAL SLOAN-KETTERING CANCER CENTER
IRB PROTOCOL

IRB#: 14-140 A (7)

Worst Toxicity CTCAE using the current active CTCAE version	Recommended Dose Modifications any time during a cycle of therapy						
Grade ≥ 3 ($> 3.0 \times \text{ULN}$)	Discontinue patient from study treatment. Note: If CTCAE Grade 3 or 4 hyperbilirubinemia is due to hemolysis, then \downarrow 1 dose level of BGJ398 and continue treatment at the discretion of the Investigator.						
AST or ALT Grade 3 ($> 5.0 - 20.0 \times \text{ULN}$) without bilirubin elevation $> 2.0 \times \text{ULN}$ Grade 4 ($> 20.0 \times \text{ULN}$) without bilirubin elevation $> 2.0 \times \text{ULN}$	Hold dose of BGJ398 until resolved to CTCAE Grade ≤ 1 or baseline 
 • If resolved in ≤ 7 days, maintain dose level of BGJ398. • If resolved in > 7 days, \downarrow 1 dose level of BGJ398. Discontinue patient from study treatment.						
AST or ALT and Bilirubin AST or ALT $> 3.0 - 5.0 \times \text{ULN}$ and total bilirubin $> 2.0 \times \text{ULN}$ without liver metastasis or evidence of disease progression in the liver AST or ALT $> 5.0 \times \text{ULN}$ and total bilirubin $> 2.0 \times \text{ULN}$	Hold dose of BGJ398 until resolved to CTCAE Grade ≤ 1 
 • If resolved in ≤ 7 days, \downarrow 1 dose level of BGJ398. • If resolved in > 7 days, discontinue patient from study treatment. Discontinue patient from study treatment.						
Laboratory / Metabolic disorders							
Asymptomatic amylase and/or lipase elevation (Note: not by CTCAE 4.0) 
  
 Grade 1 ($> \text{ULN} - 2.0 \times \text{ULN}$)	 
 • Continue BGJ398 dosing 	
 
 Grade 2 ($> 2.0 \times \text{ULN} - 5.0 \times \text{ULN}$ with no attributable clinical signs or symptoms)	 
 • May continue BGJ398 dosing; consider weekly laboratory monitoring 	
 
 Grade 3 ($> 2.0 - 5.0 \times \text{ULN}$ with attributable clinical signs or symptoms OR $> 5.0 \times \text{ULN}$ without clinical signs or symptoms)	 
 • Hold dose of BGJ398 until resolved to CTCAE Grade ≤ 2. • Consider \downarrow 1 dose level of BGJ398 	
  
 
Note: A CT scan or other imaging study to assess the pancreas, liver, and gallbladder should be considered after the first occurrence of any CTCAE \geq Grade 3 amylase and/or lipase.
		Grade 1 ($> \text{ULN} - 2.0 \times \text{ULN}$)	
 • Continue BGJ398 dosing 	Grade 2 ($> 2.0 \times \text{ULN} - 5.0 \times \text{ULN}$ with no attributable clinical signs or symptoms)	
 • May continue BGJ398 dosing; consider weekly laboratory monitoring 	Grade 3 ($> 2.0 - 5.0 \times \text{ULN}$ with attributable clinical signs or symptoms OR $> 5.0 \times \text{ULN}$ without clinical signs or symptoms)	
 • Hold dose of BGJ398 until resolved to CTCAE Grade ≤ 2. • Consider \downarrow 1 dose level of BGJ398
Grade 1 ($> \text{ULN} - 2.0 \times \text{ULN}$)	
 • Continue BGJ398 dosing 						
Grade 2 ($> 2.0 \times \text{ULN} - 5.0 \times \text{ULN}$ with no attributable clinical signs or symptoms)	
 • May continue BGJ398 dosing; consider weekly laboratory monitoring 						
Grade 3 ($> 2.0 - 5.0 \times \text{ULN}$ with attributable clinical signs or symptoms OR $> 5.0 \times \text{ULN}$ without clinical signs or symptoms)	
 • Hold dose of BGJ398 until resolved to CTCAE Grade ≤ 2. • Consider \downarrow 1 dose level of BGJ398 						

MEMORIAL SLOAN-KETTERING CANCER CENTER
IRB PROTOCOL

IRB#: 14-140 A (7)

Worst Toxicity CTCAE using the current active CTCAE version	Recommended Dose Modifications any time during a cycle of therapy

Diarrhea
 
Grade 1
 
Grade 2
 
Grade 3
 
Grade 4
	
Maintain dose level of BGJ398, but initiate anti-diarrheal treatment
 
 • Hold dose of BGJ398 until resolved to CTCAE Grade \leq 1 • Optimize anti-diarrheal treatment, maintain dose level of BGJ398. • For reoccurrence of diarrhea CTCAE Grade 2, hold dose of BGJ398 until resolved to CTCAE Grade \leq 1, ↓ BGJ398 by 1 dose level 
 • Hold dose of BGJ398 until resolved to CTCAE Grade \leq 1 • Optimize anti-diarrheal treatment • ↓ BGJ398 by 1 dose level • For reoccurrence of diarrhea CTCAE Grade 3, despite optimal anti-diarrheal treatment, discontinue patient from study treatment. 
Discontinue patient from study treatment.
 
Note: Antidiarrheal medication is recommended at the first sign of abdominal cramping, loose stools or overt diarrhea

Vomiting
 
Grade 2 not controlled by optimal anti-emetic therapy
 
Grade 3 not controlled by optimal anti-emetic therapy or Grade 4
	
Hold BGJ398 doses until \leq grade 1, ↓ 1 dose level
 
Discontinue patient from study

Eye Disorders (confirmed by ophthalmologic examination)
	

Retinal disorders
 
Grade 2 CSR and CSR-like events
 
Grade 3 CSR and CSR-like events and any other grade 3 eye disorders
 
\geq grade 1 retinal vein occlusion, grade 4 CSR and CSR-like events, and grade 4
	
Hold BGJ398 until resolved to \leq grade 1 but refer the patient to a retinal specialist for evaluation
 
 • If resolved in \leq 14 days, ↓ BGJ398 by 1 dose level • If resolved in $>$ 14 days, discontinue BGJ398 
Hold BGJ398 until resolved to grade \leq 1.
 
 • If resolved in \leq 14 days, ↓ BGJ398 by 1 dose level • If resolved in $>$ 14 days, discontinue BGJ398

MEMORIAL SLOAN-KETTERING CANCER CENTER
IRB PROTOCOL

IRB#: 14-140 A (7)

Worst Toxicity CTCAE using the current active CTCAE version	Recommended Dose Modifications any time during a cycle of therapy
other eye disorders	Discontinue BGJ398
Other ocular/visual toxicity ≥ grade 3	Hold BGJ398 until resolution to ≤ grade 1 If resolution in ≤14 days, ↓ 1 dose level, otherwise discontinue BGJ398
General disorders	
Fatigue Grade 3	Hold dose of BGJ398 until resolved to CTCAE Grade ≤ 1 
 • If resolved in ≤ 7 days, maintain dose level of BGJ398. • If resolved in > 7 days, discontinue patient from study treatment.
Other clinically significant AEs	
Grade 3	Hold dose of BGJ398 until resolved to CTCAE Grade ≤ 1, then ↓ 1 dose level of BGJ398.
Grade 4	Discontinue patient from study treatment.
All dose modifications should be based on the worst preceding toxicity. Once a dose has been reduced it will not be increased at a later time even if there is no toxicity. Patients who require more than two dose reductions of BGJ398 will be discontinued from study drug treatment. If a patient requires a dose delay of > 14 days from the intended day of the next scheduled dose of BGJ398 then study treatment must be stopped.	

Table 8: Prophylaxis and Treatment recommendations for hyperphosphatemia without kidney injury:

Hyperphosphatemia Prophylaxis (Patients receiving treatment schedule A)	Initiate Sevelamer 800 mg with meals (up to TID) concurrent with BGJ398, unless otherwise contraindicated by patient's current medical condition. Restrict dietary phosphate intake to 600 – 800 mg/day, if BMI ≥ 21kg/m ² .
Hyperphosphatemia Treatment Without Elevated Creatinine	INTERVENTION
Serum Pi > 5.5 – 7.0mg/dL:	Continue sevelamer 800 mg with 2 meals per day and increase the dose of sevelamer with the largest meal to 1600mg (total daily dose = 3200 mg).
Serum Pi 7.1mg – 9.0mg/dL	Increase the dose of sevelamer up to 1600mg (2 tablets per meal) every 8 hours and continue sevelamer through Day 21 and until Serum Pi is <5.5, whichever is later. Sevelamer should be given even on days BGJ398 is not taken until serum Pi is <5.5. If serum Pi ≤ 7.0 mg/dL within 7 days, increase sevelamer to 1600 mg TID with next cycle, if not already done so. No interruption or adjustment to BGJ398 is necessary. If Serum Pi >7.0 mg/dL for longer than 7 days, hold BGJ398 until serum Pi is <5.5 mg/dL. Assess if patients were taking Sevelamer 1600 mg TID on Day 1 of most recent cycle.

MEMORIAL SLOAN-KETTERING CANCER CENTER
IRB PROTOCOL

IRB#: 14-140 A (7)

	
 - If patient was NOT taking Sevelamer 1600 mg TID on Day 1 of the most recent cycle: 
 o Increase Sevelamer to 1600 mg TID for each subsequent cycle o No dose reduction in BGJ398 is necessary - If patient WAS taking sevelamer 1600 mg TID on Day 1 of the most recent cycle: 
 o Dose reduce BGJ398 by 1 level 
If serum phosphorous does not resolve to <7.0 mg/dL despite phosphorous lowering therapy within 14 days of first held dose of BGJ398, discontinue BGJ398 therapy. All patients will continue to be followed-up until resolution to serum phosphorus \leq 5.5 mg/dL or baseline or stabilization.

Serum Pi 9.1 mg/dL or higher
	
Recheck serum Pi as soon as possible to rule out laboratory error. If confirmed, hold BGJ398 until Serum Pi <7.0 mg/dL. Increase the dose of sevelamer up to 1600mg (2 tablets per meal) every 8 hours and continue sevelamer through Day 21 and until Serum Pi is <5.5, whichever is later. Sevelamer should be given even on days BGJ398 is not taken until Serum Pi is <5.5. Then assess:
 
 - If patient was NOT taking Sevelamer 1600 mg TID on Day 1 of the most recent cycle: 
 o Increase Sevelamer to 1600 mg TID for each subsequent cycle o No dose reduction in BGJ398 is necessary - If patient WAS taking sevelamer 1600 mg TID on Day 1 of the most recent cycle: 
 o Dose reduce BGJ398 by 1 level 
If serum phosphorous does not resolve to <7.0 mg/dL despite phosphorous lowering therapy within 14 days of first held dose of BGJ398, discontinue BGJ398 therapy. All patients will continue to be followed-up until resolution to serum phosphorus \leq 5.5 mg/dL or baseline or stabilization.

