9.2 Follow-up for toxicities

Patients whose treatment is interrupted or permanently discontinued due to an adverse event or clinically significant laboratory value must be followed until resolution or stabilization of the event. Appropriate clinical experts (e.g. ophthalmologist, cardiologist, dermatologist) should be consulted as deemed necessary. A dose interruption of ≥ 28 days may require the patient to be discontinued from the study (with the exception of patients who undergo surgery; see section 13). Patients will continue to be followed for toxicity for 28 days following the last dose of study medication.

Patients exhibiting hypomagnesaemia, hypocalcaemia, and/or hypokalemia, should receive electrolyte replacement as indicated by national and institutional guidelines and be followed until laboratory values have normalized or as clinically indicated.

Patients on the study will be examined regularly to monitor for the possible development of CSR, as the appearance of CSR has been associated with BGJ398 treatment. Patients will receive an ophthalmological visit at baseline and 4 weeks after initiation of the study drug. If an ocular event occurs, patients will undergo ophthalmological evaluation as mandated by the study ophthalmologist. For patients developing a CSR of any grade it is recommended to follow up the CSR with an ophthalmological exam every two weeks for 8 weeks, and subsequently at approximately a 4-

MEMORIAL SLOAN-KETTERING CANCER CENTER
IRB PROTOCOL

IRB#: 14-140 A (7)

week interval. Dose adjustments for ocular toxicities are outlined in Table 11. If ocular findings re-develop after rechallenge with drug, drug may be permanently discontinued based on evaluation by the study ophthalmologist.

All patients will have baseline cardiac ejection fraction evaluated by echocardiogram or MUGA studies. If a cardiac event occurs, the patients will undergo cardiac evaluation as seen appropriate by the investigator.

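### Table 7 gives opposite instructions for a grade 4 eye disorder, other than CSR or retinal vein occlusion, that resolves within 14 days: discontinue BGJ398, or restart one dose level lower

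*Combined protocol and SAP*

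**What the plan says.** The Eye Disorders part of Table 7 in section 9.3.2 has two blocks.

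The first is labelled as retinal disorders, but its entries reach further:

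- Its grade 3 entry is "Grade 3 CSR and CSR-like events and any other grade 3 eye disorders". BGJ398 is held until grade 1 or lower, reduced one level if that takes 14 days or less, and otherwise stopped.
- Its last entry covers retinal vein occlusion from grade 1 upward together with grade 4 events: "grade 1 retinal vein occlusion, grade 4 CSR and CSR-like events, and grade 4". The text runs over a page break and ends with other eye disorders. The action is to discontinue BGJ398, with no condition on recovery time.

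The second block is a single row, "Other ocular/visual toxicity ≥ grade 3". BGJ398 is held until grade 1 or lower, restarted one level down if that happens within 14 days, and otherwise discontinued.

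The note that closes the table says "All dose modifications should be based on the worst preceding toxicity". Section 9.2 adds: "If an ocular event occurs, patients will undergo ophthalmological evaluation as mandated by the study ophthalmologist".

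**The concern.** A stopping rule should give one answer for one event. Here a site facing a grade 4 eye disorder outside the two named categories could stop BGJ398 permanently or re-expose the patient at a lower dose, and either action would comply with the table. In a multi-center trial, two sites could treat the same event in opposite ways. What is at stake is re-exposure after the more severe grade of ocular toxicity, with a drug already known to affect the eye. The response endpoint is not in question.

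**Working it through.** No arithmetic applies. The check sets the triggers and actions side by side and then looks for a rule of precedence.

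**Step 1: compare the rows** for an eye disorder that is neither CSR/CSR-like nor retinal vein occlusion.

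| Event | First block | Last eye row | Agree? |
|---|---|---|---|
| Grade 3, down to grade 1 or lower in 14 days or less | Reduce one level | Reduce one level | Yes |
| Grade 3, takes longer than 14 days | Discontinue | Discontinue | Yes |
| Grade 4, down to grade 1 or lower in 14 days or less | Discontinue | Reduce one level | **No** |
| Grade 4, takes longer than 14 days | Discontinue | Discontinue | Yes |

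The conflict is confined to one cell. At grade 3 the last row only repeats the action given above it.

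**Step 2: rule out a reading error.** The page break falls between the words for grade 4 and the words for other eye disorders. The continuation and its action cell are both legible, so the overlap is in the table itself.

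**Step 3: look for a tie-breaker.**

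- The closing note, "All dose modifications should be based on the worst preceding toxicity", says which toxicity to act on. It does not choose between two rows that the same event meets at the same grade.
- Section 9.2 refers the reader to Table 11 for ocular dose adjustments. Table 11 is the phase II visit schedule and contains no such rule.
- Section 9.3.2 allows exceptions: "In exceptional situations, study treatment may continue even if the patient experienced one of the treatment stopping rules". That clause starts from a stopping rule that has been met, and whether one has been met is the open question.
- The eye section requires ophthalmologic confirmation. This establishes the event, not the dosing action.
- The general grade 4 entry under "Other clinically significant AEs" leads to discontinuation. It agrees with the first block but does not say that it overrides a specific eye row.

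None of these decides the matter.

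**The case against.** The strongest reply is that an ordinary reading removes the overlap. There are two candidates:

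- *Other* in the last row may mean events not already covered. The row is then redundant, and grade 4 means stop.
- The retinal label may limit the first block. Table 3 does separate retinal events from visual disturbances without retinal changes, so each row could have been meant for its own kind of event. A non-retinal grade 4 event could then restart.

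Each is a reasonable guess at intent, but they give opposite actions for the same non-retinal grade 4 event, so together they show that the rule is unclear. The second also goes against the wording, since the first block speaks of eye disorders generally at both grade 3 and grade 4.

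What does stand is the argument about weight. The table is introduced as guidance and its action column is headed as recommendations. Evaluation by the study ophthalmologist is required after an ocular event. Section 9.2 also foresees ocular findings recurring on rechallenge and allows permanent discontinuation on that ophthalmologist's evaluation. These safeguards lower the risk without choosing between the rows.

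**Conclusion.** The conflict is real and narrow, and warrants a minor safety correction. It arises only for a grade 4 eye disorder outside CSR/CSR-like events and retinal vein occlusion that reaches grade 1 or lower within 14 days. This rests on reading the last row's open-ended grade range as including grade 4, which is its plain meaning. Confidence is high that the rows overlap, and lower about which action was intended.

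A reader might infer three stronger points that the documents do not support:

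- *A rate.* Section 11.1.2 reports eye events among the 94 BGJ398 monotherapy patients, and one could turn them into a percentage. None is stated to be grade 4. Two of them, the retinal detachment and the punctate corneal epitheliopathy, are listed among events for which patients stopped treatment. The frequency of the conflict is unknown.
- *A special gap after cycle 1.* The Table 3 criteria serve dose escalation. Table 7 applies at any time during a cycle, including cycle 1, so the conflict is the same throughout.
- *A uniform rule that grade 4 means stop.* Table 7 often works that way, but not always. The bilirubin note, "If CTCAE Grade 3 or 4 hyperbilirubinemia is due to hemolysis", allows treatment to continue at a lower dose. The entries for QTcF above 500 msec and for asymptomatic amylase or lipase above 5 times the upper limit have no upper bound and allow restart. The table's pattern favours discontinuation without proving that it was intended.

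**What to change.** Change the last eye row in Table 7 from grade 3 or higher to grade 3, or delete the row, since the grade 3 entry above it already gives the same action. Every grade 4 eye disorder then leads to discontinuation, in line with the grade 4 rule for "Other clinically significant AEs". Rare continuation would still be possible through the existing case-by-case discussion with the MSKCC principal investigator.

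The clinical team should confirm this direction. If they want non-retinal grade 4 events to remain eligible for restart, the first block's wording should be narrowed to retinal disorders instead.

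The cost is one phrase in a protocol amendment. Sample size, assessments and analysis do not change.
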